3.2 Trial setting

The trial will be conducted in approximately 20 NHS sites across the UK (secondary/ primary/ community settings). Potential participants will be identified directly by participating research sites. Participating research sites may also utilise Patient Identification Centres (PIC) to identify potentially eligible patients.

Participants will undergo a baseline visit and 52-week follow-up visit at the NHS research site. During these visits all participants will be required to complete a questionnaire and CRF, provide an exhaled CO reading, spirometry reading and a blood sample. Behavioural support telephone calls (at -1, 0, +1, +2, +3 and +4-weeks post TQD) will be delivered to all participants over the phone or via video call by the Health and Lifestyle Research Unit at the Wolfson Institute of Population Health, Queen Mary University of London.

The 4 and 26-week follow up will also be conducted over the phone or via video call by the Health and Lifestyle Research Unit, if uncontactable a follow up questionnaire will be sent to the participant by post/email.

3.3 Sub-studies

In addition to the main RCT, there will be the following embedded cohort studies:

- (1) Lung health sub-study
- (2) Wellbeing sub-study

These will be conducted once all follow up is complete and the database is locked for analysis. For both of the cohort analyses, participants from the trial will be re-categorised into the following exposure groups based on their smoking and vaping status during the trial, assessed at 52 weeks:

- Vaper (switched to exclusive EC use)
- Smoker (continued to smoke)
- Quitter (quit smoking and did not vape)

For lung health, the analysis will compare change in clinical, physiological and cellular lung health measures and toxicant levels in vapers, smokers and quitters. Cellular and toxicant outcomes will be measured in blood samples taken from participants when they attend the research site at baseline and 52 weeks. As it is not possible to know which participants will fall into each of these exposure groups when the blood is taken, blood will be taken from all participants. Blood

samples not used will be banked for future studies (subject to participant consent). The blood measures have been funded by the NIHR EME funding stream.

For wellbeing, the analysis will compare change in anxiety, depression and social quality of life in vapers, smokers and quitters.

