1. BACKGROUND AND RATIONALE

1.1 Background

COPD and smoking Chronic obstructive pulmonary disease (COPD) is a common lung condition which affects around 2 million people in the United Kingdom (UK).² It is currently the fourth most common cause of death worldwide,³ and death rates are rising. It is projected to become the leading cause of death worldwide by 2035.⁴ Patients with this condition experience symptoms including breathlessness, cough, increased sputum production and acute periods of exacerbation of their symptoms which may lead to hospitalisation. Lung function (specifically airflow obstruction) defines disease severity with patients experiencing a decline as the disease progresses. In developed countries, cigarette smoking is the most common cause of COPD, and continued smoking by people with COPD is known to accelerate decline in lung function. Smoking cessation is the only known strategy that limits this acceleration³, and therefore smoking cessation is a priority for these patients.

Guidance from the National Institute for Health and Care Excellence (NICE) recommends that COPD patients who are still smoking should be encouraged to quit at every opportunity and offered help to do so.⁵ However, prevalence of smoking in COPD patients in the UK remains much higher than in the general population, with estimates as high as 35%.^{6,7} COPD patients are generally more heavily addicted to smoking and find it harder to quit,⁸ and experience disproportionately larger adverse health effects from their smoking than the general population.⁹ Even when using effective NICE recommended treatments to support a quit attempt, success rates are low with over 80% relapsing within a year.^{11,12}

Electronic cigarettes Electronic cigarettes (ECs) are commercially available products that vaporise a liquid which usually contains nicotine and is inhaled by the user.¹³ They have emerged as a viable alternative to cigarette smoking, with considerable potential to replace and eventually eradicate conventional cigarettes.¹⁴ In the UK in 2021, an estimated 3.6 million adults used ECs, and of these 2 million had completely stopped smoking.¹⁵ Survey evidence shows that people with COPD are using ECs to help them stop smoking, however there remain unanswered questions regarding their effectiveness for smoking cessation and the potential effects of use on health in this patient group.

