1.3.3 Justification for design

To definitively test the effectiveness and cost-effectiveness of EC for smoking cessation compared with NRT in COPD patients, a randomised controlled trial (RCT) is required with embedded economic analysis.

To investigate the effect of switching to vaping on lung health and wellbeing, a cohort analysis is necessary. For the cohort analysis, participants will be re-grouped based on their smoking and vaping status throughout the trial into vapers, quitters or smokers, rather than being analysed by trial arm. This is necessary as many people in each arm of the trial will relapse back to smoking, and therefore analysis by trial arm will not show the effect of vaping, quitting or smoking on lung health/wellbeing as trial arms will contain a mixture of these.

1.3.4 *Justification for choice of intervention*

We will be using a modern EC starter pack which will include an initial supply of e-liquid. There is no recommended length of use of ECs for smoking cessation as is the case for NRT where up to 12 weeks is recommended. Participants will therefore be given an initial supply of a sufficient amount to start using the EC (up to 20 mg nicotine/ml) and then advised to source continuing supplies. Participants will be advised how to continue sourcing supplies according to preference which may include changing devices, flavours and strengths as needed. This strategy was used successfully in our previous trials.^{30 55}

ECs will be compared with up to 12 weeks supply of combination NRT. Participants will be encouraged to use a nicotine patch in combination with a fast-acting product (e.g. gum, lozenge, microtab) as this has been shown to be the most effective way of using NRT⁵⁶ and is recommended by NICE.⁵⁴ Taking a pragmatic approach, should participants indicate they are not able to use the patch (e.g. due to previous reactions to nicotine patch), they will be able to choose two fast-acting products. Choice of fast-acting nicotine product for all participants will also be dependent on product availability.

1.3.5 *Justification of choice of primary outcome*

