9.2.2 Secondary outcomes

1. Abstinence from smoking for at least 26 weeks biochemically validated (exhaled CO < 8 ppm) at 52 weeks
2. 7-day point prevalence abstinence from smoking biochemically validated (exhaled CO < 8 ppm) at 52 weeks
3. Self-reported abstinence from smoking for at least 26 weeks at 52 weeks

-
4. Self-reported 7-day point prevalence abstinence from smoking at 4, 26 and 52 weeks
 5. Reduction in cigarettes smoked (self-report of any and > 50% reduction from baseline to 52 weeks, confirmed by reductions in expired CO readings at 52 weeks)
 6. Reduction in cigarettes smoked (self-report of any and > 50% reduction from baseline to 26/52 weeks)
 7. Continued use of allocated product at 4, 26 and 52 weeks
 8. Withdrawal symptoms and urges to smoke (change from baseline to 1/ 2/ 3/ 4 weeks) measured using the mood and physical symptom scale (MPSS)
 9. COPD Symptoms (change from baseline to 4/ 26/ 52 weeks) measured using COPD Assessment Test (CAT) and the Clinical COPD Questionnaire (CCQ)
 10. Number of COPD exacerbations over the past 52 weeks (from baseline to 52 weeks)
 11. Number of self-reported upper respiratory tract infections over the past 52 weeks (from baseline to 52 weeks)
 12. Post bronchodilator spirometry (FEV₁, FVC and MMEF change from baseline to 52 weeks)
 - Forced Expiratory Volume in 1 Second (FEV₁): The maximal volume of air that can be expired in the first second of a forced expiration from a position of full inspiration (measured in Litres (L) and also expressed as the % predicted for age, sex, height and race)
 - Forced Vital Capacity (FVC): The maximal volume of air that can be expired during a forced and complete expiration from a position of full inspiration (measured in L and % predicted)
 - Mean Mid-Expiratory Flow (MMEF): The average flow between 25% and 75% of the FVC manoeuvre (measured in L/sec and % predicted)

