9.3 Health economic outcomes

1. Health-related quality of life (EQ-5D-5L) (change from baseline to 4/ 26/ 52 weeks)
2. Use of healthcare resources and costs (measured at 26 and 52 weeks)
3. Cost-effectiveness based on cost per quitter and cost per Quality-Adjusted Life-Year (QALY) at 52 weeks, and modelled cost per QALY over patient lifetime

9.4 Lung health sub-study outcomes (subset of participants included in the cohort analysis only):

1. COPD Symptoms (change from baseline to 4/ 26/ 52 weeks) measured using COPD Assessment Test (CAT) and the Clinical COPD Questionnaire (CCQ)
2. Health-related quality of life (EQ-5D-5L) (change from baseline to 4/ 26/ 52 weeks)
3. Number of COPD exacerbations over the past 52 weeks (from baseline to 52 weeks)
4. Self-reported upper respiratory tract infections over the past 52 weeks (change from baseline to 52 weeks)

5. Post bronchodilator spirometry (FEV₁, FVC and MMEF change from baseline to 52 weeks)
 - Forced Expiratory Volume in 1 Second (FEV₁): The maximal volume of air that can be expired in the first second of a forced expiration from a position of full inspiration (measured in Litres (L) and also expressed as the % predicted for age, sex, height and race)
 - Forced Vital Capacity (FVC): The maximal volume of air that can be expired during a forced and complete expiration from a position of full inspiration (measured in L and % predicted)
 - Mean Mid-Expiratory Flow (MMEF): The average flow between 25% and 75% of the FVC manoeuvre (measured in L/sec and % predicted)
6. Full blood count (total and differential white blood cell (WBC) count x10⁹/L) (change from baseline to 52 weeks)
7. Serum/plasma biomarkers such as but not restricted to cytokines such as IL-6, IL-8, TNF- α ; antimicrobial peptides; and markers of proteinase activity (change from baseline to 52 weeks)
8. Toxicant analysis; to include toxicants such as formaldehyde, acetaldehyde, acrolein (change from baseline to 52 weeks)

9.5 Wellbeing sub-study outcomes (subset of participants included in the cohort analysis only):

1. Anxiety - Hospital Anxiety and Depression Scale (HADS) (change from baseline to 52 weeks)
2. Depression - HADS (change from baseline to 52 weeks)
3. Mixed anxiety and depression - EQ-5D-5L (change from baseline to 52 weeks)
4. Breathing related depression and social quality of life - CCQ (change from baseline to 52 weeks)

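### The 4- and 26-week lung-health contrasts compare exposure groups formed with information up to 52 weeks, so they condition on behaviour after the outcome

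*Protocol*

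**What the plan says.** Section 3.3 sets the timing of the sub-studies: "These will be conducted once all follow up is complete and the database is locked for analysis". Participants are then re-categorised as vapers, smokers or quitters "based on their smoking and vaping status during the trial, assessed at 52 weeks". One set of groups is described, with no separate set for each visit.

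Section 1.3.3 words the basis differently: "participants will be re-grouped based on their smoking and vaping status throughout the trial into vapers, quitters or smokers".

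Section 9.4 lists the lung-health outcomes for these groups. The first is "COPD Symptoms (change from baseline to 4/ 26/ 52 weeks) measured using COPD Assessment Test (CAT) and the Clinical COPD Questionnaire (CCQ"). EQ-5D-5L change has the same three visits. Exacerbations and upper respiratory infections are counted over the whole 52 weeks. Spirometry, blood counts, biomarkers and toxicants are changes from baseline to 52 weeks only. The footnote to Appendix 1 confirms that sub-study outcomes are compared by exposure group.

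Section 17 admits to the cohort those who meet the criteria for one of the three groups, plans adjustment for confounders and (in linear regression) the baseline value, and leaves further detail to a separate cohort SAP.

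Section 9.2.2 shows that interim status is collected: "Self-reported 7-day point prevalence abstinence from smoking at 4, 26 and 52 weeks", together with continued use of the allocated product at the same visits.

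**The concern.** The sub-study is meant to estimate what switching to vaping does to lung health, compared with quitting without vaping and with continued smoking. For a symptom score at week 4 or 26, the relevant exposure is what the participant had been doing up to that visit. Groups formed with information up to week 52 also use the following 48 or 26 weeks.

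Two faults can follow:

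- **Selection.** If people whose symptoms improve early are more likely to stay abstinent, or people whose symptoms worsen are more likely to quit later, early symptoms help to determine group membership. The groups then differ at the early visit whether or not exposure had any effect. The symptom change arises after baseline, so the adjustment in section 17 does not remove this.
- **Dilution.** If the groups rest on status at week 52 alone, someone abstinent at weeks 4 and 26 who later relapsed counts as a smoker throughout. Someone who quit in month 11 counts as a quitter or vaper throughout, including in the year's exacerbation count.

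Early symptom differences could then be reported as effects of vaping or quitting when they partly reflect who went on to relapse.

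**Working it through.** **The plan's own figure.** The protocol gives no size or power for the cohort analyses. Its one calculation is the main-trial sample size, which this point does not touch. With 8% v 14%, two-sided 5% and 90% power, the pooled formula gives n = 570 per arm. With continuity correction, (570/4) × [1 + √(1 + 4/(570 × 0.06))]² = 603, as stated. Then 1206/0.97 = 1243.3, so 1244, rounded up to 1250. Only the average rate, (8% + 14%)/2 = 11%, is borrowed below.

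**Is change of status expected?** Yes. Section 1.3.3 expects many in each arm to relapse, and section 1.1 says of existing treatments that "success rates are low with over 80% relapsing within a year".

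**Reading 1: point status at 52 weeks.** Let f be the share of the 52-week quitter or vaper group still smoking at week 4, and g the share of the 52-week smoker group abstinent at week 4. The share of a true week-4 contrast that is retained is 1 − f − g.

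| f | g | retained |
|---|---|---|
| 0 | 0 | 1.00 |
| 0.10 | 0.20 | 0.70 |
| 0.25 | 0.40 | 0.35 |

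The protocol gives neither f nor g. To show a range for g, take 11% as the non-smoking share at week 52, count the other 89% as smokers, and assume a share A is abstinent at week 4, including all of the 11%. Then g = (A − 0.11)/0.89, which is 0.16, 0.27 and 0.38 for A = 0.25, 0.35 and 0.45. A is an assumption, and placing all 89% in the smoker group ignores missing status and anyone who meets no group's criteria.

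**Reading 2: sustained status, with mixed histories left out.** Members already had their status at week 4, so f = g = 0 and nothing is diluted. Selection remains. Let y be week-4 improvement in SD units, standard normal, with no effect of exposure. Let the chance that a week-4 abstainer stays abstinent be expit(a + y ln OR), with a set so that the average is 0.11/A. Continuous smokers have mean y = 0, so the spurious difference is the mean of y among those who stay. With OR = 1.5 per SD:

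| A | 0.11/A | spurious difference |
|---|---|---|
| 0.25 | 0.44 | 0.22 SD |
| 0.35 | 0.31 | 0.27 SD |
| 0.45 | 0.24 | 0.30 SD |

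At OR = 1 the difference is 0.

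**The direction is open.** Take week 26 under reading 1 with no true effect. Assume 17% are abstinent, 5% of the smokers quit later and 35% of the abstainers relapse. Per 100 participants, 83 × 0.05 = 4.15 are late quitters and 78.85 remain smokers; 17 × 0.35 = 5.95 relapse and 11.05 stay abstinent. The 52-week groups are 15.20 non-smokers and 84.80 smokers. To first order, an odds ratio of 1.5 shifts the mean of those who change by 0.405 × (1 − p) SD and of those who do not by −0.405 × p, where 0.405 = ln 1.5 and p is the share who change.

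- Worse symptoms prompt late quitting: non-smokers (4.15/15.20) × 0.385 = 0.105; smokers (78.85/84.80) × (−0.020) = −0.019; difference about +0.12 SD, so non-smokers look worse.
- Worse symptoms prompt relapse: non-smokers (11.05/15.20) × (−0.142) = −0.103; smokers (5.95/84.80) × 0.264 = 0.019; difference about −0.12 SD, so non-smokers look better.

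**The case against.** The strongest reply is that the protocol does not define the groups by status on the day of the 52-week visit. A reader might infer that it does, and that the early contrasts are therefore bound to be diluted. The documents do not support that. Section 3.3 speaks of status during the trial and can be read as naming the visit at which that history is ascertained. Section 1.3.3 says status throughout the trial, the smoker label describes someone who carried on smoking, and section 17 admits only those who meet a group's criteria. On that reading, the participant who relapses after week 26 and the one who quits in month 11 may belong to no group, and the dilution disappears. This part of the reply stands.

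A reader might also take the illustrative figures above as estimates for this trial. They are not. The abstinence shares at weeks 4 and 26 and the odds ratios are assumptions, and the sign changes with them.

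The third argument is that the criteria are left to the cohort SAP. The exact criteria, the handling of switchers and the model can be left there. But the protocol already states that one set of groups is formed with information up to 52 weeks, and that the early outcomes are compared between them. A SAP that used visit-specific status would depart from section 3.3.

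Finally, the scope is narrow. That is correct and is reflected in the verdict.

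**Conclusion.** The point holds in a limited form. As written, the 4- and 26-week CAT, CCQ and EQ-5D-5L contrasts condition on behaviour after the outcome, whether group status is point or sustained, and the planned adjustment does not correct this. Bias arises if early symptoms influence later relapse or quitting, which is plausible but not shown in the documents. Its size and direction cannot be derived from them; the 0.1 to 0.3 SD illustrations depend on the assumed abstinence shares and an assumed odds ratio of 1.5 per SD.

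Dilution of the early contrasts, and months of smoking carried into the quitter or vaper event counts, follow only if status at week 52 alone defines the groups. Sections 1.3.3 and 3.3 leave that unsettled and should be reconciled.

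The randomised main-trial analysis, its sample size and its power are unaffected. The wellbeing outcomes are measured at 52 weeks only and escape the early-outcome problem, as do spirometry and the blood measures. The correction should be made before the cohort SAP is final.

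**What to change.** Amend sections 3.3 and 17, and align section 1.3.3:

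1. Compare the 4- and 26-week lung-health outcomes by smoking and vaping status up to that visit, never by later status. Self-reported abstinence and allocated-product use are collected at both visits (section 9.2.2). The sensitivity analyses in section 15.4 also need data on non-allocated products. Check that the 4- and 26-week forms record vaping in the NRT arm well enough to identify exclusive vapers at those visits.
2. State that the groups for the 52-week outcomes and whole-year event counts require status sustained over the period counted. A minimum of 26 weeks' abstinence would not be enough for the counts, since someone who quit at week 26 would still bring 26/52, or half a year, of smoking into the quitter or vaper group.
3. Keep point status at 52 weeks as a sensitivity analysis.

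The cost is protocol and cohort-SAP wording, with no change to the sample size. The downsides are that group membership differs by visit, interim status is self-reported without CO validation (CO is measured only at baseline and 52 weeks), and the sustained groups are smaller.

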3.4 Assessment of risk

All clinical trials can be considered to involve an element of risk and in accordance with the Birmingham Clinical Trials Unit (BCTU) standard operating procedures this trial has been risk assessed to clarify any risks relating uniquely to this trial beyond that associated with usual care. A Risk Assessment has been conducted and concluded that this trial corresponds to the following categorisation: Type A = No higher than the risk of standard medical care.

This trial is considered to be a low-risk Clinical Trial of an Investigational Medicinal Product (CTIMP). Nicotine Replacement Therapy products constitute the IMP and will be used on-label. The EC is a consumer product regulated under the Tobacco and Related Product Regulations. We will be providing an EC starter pack to allocated participants, but they will be permitted within the trial to purchase a different EC device and/or e-liquid if the one provided does not work for them. This has worked in our previous trials and is the current approach used by stop-smoking services who provide EC starter packs as part of standard care and encourage clients to switch to other EC products if needed.

The wellbeing sub-study will utilise measures which assess depression and anxiety. This may identify people at risk i.e., a HADS scoring of ≥ 11 and/or may prompt disclosure of other mental health related issues of concern. The PI will be notified in these circumstances and local site process will be followed.

4. PATIENT IDENTIFICATION AND INVITATION

There are a number of methods available to identify potentially eligible patients and invite them to take part in the trial. This is to maximise the ability to recruit to the required target. These methods are summarised in table 1 and described in detail in the sections below.

Table 1: Summary of method options to identify potentially eligible patients, invite them to take part in the trial and complete the pre-baseline check

	Method of identification	Method of invitation and pre-baseline check
At a research site	Patient is approached face to face by direct care team	
If the patient is interested in taking part in the trial they will complete the pre-baseline check face to face. The pre-baseline check will be conducted by the direct care team but can be supported by the BCTU trial office or QMUL trial team. Upon confirming the patient meets the minimum trial entry criteria, the patient will be booked in for the baseline appointment by the site
 
Alternatively, a patient can be given an invitation pack (paper or online). If interested the patient will complete the reply slip (paper or online) which is sent to BCTU (by post or online) who will then contact the patient, or hand over to QMUL or relevant site to complete the pre-baseline check. Upon confirming the patient meets the minimum trial entry criteria, the patient will be booked in for the baseline appointment by the site.

	Patient sees advertisement and decides to express an interest	
The advertisement will provide a link to the online invitation pack. If interested the patient will complete an online reply slip which is sent to BCTU. Patients who return a reply slip will be contacted by BCTU, QMUL or relevant site, to complete the pre-baseline check. Upon confirming the patient meets the minimum trial entry criteria, the patient will be booked in for the baseline appointment by the site.
 
Alternatively, trial advertisements will provide the email & phone number for the trial office so patients can ask questions and express an interest directly, if they prefer. BCTU, QMUL or relevant site will complete the pre-baseline check. Upon confirming the patient meets the minimum trial entry criteria, the patient will be booked in for the baseline appointment by the site.

	Patient identified by other means (e.g. clinic lists/medical records)	
Patients may receive a phone call inviting them to take part in the trial and/or will be sent an invitation pack by post (paper) or by text (online), by their direct care team. If interested the patient will complete the reply slip (paper or online) which is sent to BCTU (by post or online) who will then contact the patient, or hand over to QMUL or relevant site, to complete the pre-baseline check. Upon confirming the patient meets the minimum trial entry criteria, the patient will be booked in for the baseline appointment by the site.
 
There will be a reminder invite or phone call after approximately 2 weeks.

At a patient identification Centre (PIC)	Patient sees advertisement and decides to express an interest	
The advertisement will provide a link to the online invitation pack. If interested the patient will complete an online reply slip which is sent to BCTU. Patients who return a reply slip will be contacted by BCTU, QMUL or relevant site, to complete the pre-baseline check. Upon confirming the patient meets the minimum trial entry criteria, the patient will be booked in for the baseline appointment by the site.

ECAL: Protocol

		Alternatively, trial advertisements will provide the email and phone number for the trial office so patients can ask questions and express an interest directly, if they prefer. BCTU, QMUL or relevant site, will complete the pre-baseline check and upon confirming the patient meets the minimum trial entry criteria, the patient will be booked in for the baseline appointment by the site.
	Patient identified through clinic lists/medical records search	Patient is sent an invitation pack by post (paper) or by text (online) or approached in person by their direct care team. If interested the patient will complete the reply slip (paper or online) which is sent to BCTU (by post or online) who will then contact the patient, or refer to the QMUL or relevant site, to complete the pre-baseline check. Upon confirming the patient meets the minimum trial entry criteria, the patient will be booked in for the baseline appointment by the site. There will be a reminder invite or phone call after approximately 2 weeks.
Identification by self-referral	Patient approached and/or provided with information about the trial via social media, Be Part of Research Volunteer Service (BPORVS) and wider care settings, i.e. community organisations and charities	Information about the trial will be advertised/ promoted to members of the public and those who feel they meet the trial requirements will be able to self-refer into the trial by completing a reply slip (paper or online) which is sent to BCTU (by post or online) who will then contact the patient, or refer to the QMUL or relevant site, to complete the pre-baseline check and book the patient in for the baseline appointment. Where postal invites are sent a reminder letter or reminder phone call may be given after approximately 2 weeks.

